6.4 STUDY TREATMENT COMPLIANCE

When participants self-administer study treatment at home, compliance with study treatment will be assessed.

At each clinic visit, participants will return all previously dispensed 70-mL bottles and all leftover fenebrutinib (or placebo) tablets. The site will count the leftover study drug tablets and assess compliance during DBT and during the OLE. Refer to the pharmacy manual for detailed instructions on drug storage and administration.

Details on treatment administration (e.g., dose and timing) should be noted in the source documents and on the Study Drug Administration electronic Case Report Form (eCRF). Cases of overdose, medication error, drug abuse, or drug misuse, along with any potential associated adverse events, should be reported as described in [Appendix 3](#).

6.5 DOSE MODIFICATION

Modification of the fenebrutinib/placebo dose is not permitted.

6.6 CONTINUED ACCESS TO STUDY TREATMENT AFTER THE END OF THE STUDY

Participants may be eligible to receive fenebrutinib as part of an extension study within the current protocol, as described in Section 4.1. In addition, participants will be moved to a program level OLE (separate protocol, protocol number TBD) as soon as it is available. The Roche Global Policy on Continued Access to Investigational Medicinal Product is available at the following website:

http://www.roche.com/policy_continued_access_to_investigational_medicines.pdf

6.7 TREATMENT OF OVERDOSE

An overdose is the administration of a drug in a quantity that is higher than the assigned dose. There is no known antidote for treating an overdose. Cases of overdose, along with any associated adverse events, should be reported as described in Appendix 3.

In the event of an overdose, the investigator should take the following steps:

1. Contact the Medical Monitor immediately.
2. Closely monitor the participant for any adverse event or serious adverse event and laboratory abnormalities until fenebrutinib can no longer be detected systemically (at least 5 days).
3. Obtain a plasma sample for PK analysis within 2 days from the date of the last dose of study treatment if requested by the Medical Monitor (determined on a case-by-case basis).

Decisions regarding dose interruptions or modifications will be made by the investigator in consultation with the Medical Monitor on the basis of clinical evaluation of the participant.

6.8 CONCOMITANT THERAPY

Previous treatment with anti-CD20 therapy (e.g., rituximab, ocrelizumab) should be reported up to 3 years prior to randomization and other MS disease modifying therapies (DMTs) should be reported up to 1 year prior to randomization. Receipt of any prior SARS-CoV-2 vaccine should be recorded in the concomitant medications eCRF. All other medications (e.g., prescription drugs, MS symptomatic therapies, over-the-counter drugs, vaccines, herbal or homeopathic remedies, nutritional supplements) and non-medicinal treatments (e.g., physiotherapy, occupational therapy) used by the patient within 3 months prior to initiation of study treatment will be recorded in the appropriate eCRF along with the following information:

- Reason for use
- Dates of administration, including start and end dates
- Dosage information, including dose and frequency

The Medical Monitor *may be consulted* if there are any questions *related to* concomitant or prior therapy.

Paracetamol or acetaminophen, at doses of ≤ 2 grams/day is permitted for use any time during the study.

6.8.1 Permitted Therapy

In general, investigators may manage a participant's care (including preexisting conditions) through use of supportive therapies, as clinically indicated and per local standard practice, with the exception of prohibited therapies defined in Section 6.8.3. and taking into account cautionary therapies defined in Section 6.8.2.

6.8.1.1 Oral Contraceptives and Hormone-Replacement Therapy

Participants who use oral contraceptives or hormone-replacement therapy can continue their use. All concomitant medications should be reported to the investigator and recorded on the appropriate eCRF. Participants using hormone-replacement therapy will be encouraged to use the minimal dose required to control their symptoms.

6.8.1.2 Symptomatic Treatments of Multiple Sclerosis

Participants requiring symptomatic treatment for MS (e.g., fampridine) and/or physiotherapy must be treated at a stable dose/regimen prior to the initiation of study drug and must have a plan to remain at a stable dose/regimen for the duration of the 12-week randomized controlled period. Concomitant treatments for symptoms related to MS should be kept constant throughout the randomized controlled period, but could be adapted according to patient's needs.

Participants must not start or modify their symptomatic treatment within 4 weeks of randomization. Symptomatic treatment may be initiated during the trial at the discretion of the investigator and should be kept at a stable dose as much as possible.

6.8.1.3 Treatment of Relapses

Participants who experience a relapse during the study may receive treatment with IV or oral corticosteroids, if judged to be clinically appropriate by the investigator. The following standardized treatment regimen may be used as warranted, 1 g/day IV methylprednisolone or equivalent dosing or oral steroid for a maximum of 5 consecutive days. At the discretion of the investigator, corticosteroids may be stopped abruptly or tapered over a maximum of 10 days. Such participants should not discontinue the treatment period solely based on the occurrence of a relapse, unless the patient or investigator feels he or she has met the criteria for withdrawal.

6.8.2 Cautionary Therapy

6.8.2.1 Acid-Reducing Agents

The solubility of fenebrutinib is pH-dependent, and absorption is negatively impacted by acid-reducing agents, such as PPIs and H2RAs, thereby decreasing systemic exposure.

Participants who use antacids (e.g., bismuth subsalicylate, calcium carbonate, aluminum-magnesium hydroxide) for symptomatic relief of heartburn should take fenebrutinib (or placebo) at least 2 hours before or 2 hours after antacid administration because gastric acid improves fenebrutinib absorption.

Participants may be treated with PPIs or H₂RAs at up to the maximum recommended dose in accordance with the local label. The dose should remain stable for at least 2 weeks prior to initiation of study treatment and throughout study treatment.

Standalone doses of acid-reducing agents at visits requiring PK sampling is prohibited (see [Table 3](#)). Any use of PPIs, H₂RAs, and/or other antacids should be recorded as concomitant medications, including the date and time of last administration.

6.8.2.2 CYP3A- and Breast Cancer Resistance Protein-Mediated Drug Interactions

The results of a clinical drug-drug interaction study (GP39616) suggest that fenebrutinib can be classified as a mild inhibitor of CYP3A at clinically relevant doses. It is possible that fenebrutinib inhibition of CYP3A may alter the metabolism of CYP3A substrates and result in increased plasma concentrations of CYP3A substrates. Therefore, medications that are sensitive CYP3A substrates should be used with caution.

The use of hormone-replacement therapy or hormonal contraceptives containing the CYP3A substrate ethinylestradiol (with the concomitant use of a barrier method) is permitted; however, these agents should be used with caution, and participants should be counseled regarding the potential risks and benefit of these medications per the local prescribing information.

In addition, the results of Study GP39616 indicate that fenebrutinib is a moderate inhibitor of the breast cancer resistance protein (BCRP; also known as ABCG2) transporter at clinically relevant doses. There is a potential for increased plasma concentrations of drugs that are known to be substrates of the BCRP transporter. Plasma concentrations of the medications that are BCRP substrates may increase; therefore, such medications should be used with caution.

The investigator may consult the Internet reference provided below to determine whether a certain medication interacts with CYP3A or BCRP. The Internet reference is not necessarily comprehensive, and the investigator should consult local prescribing information for the concomitant medication when determining whether a concomitant medication can be safely administered with study treatment. In addition, the investigator should contact the Medical Monitor (or delegate) if questions arise prior to concomitant administration with study treatment.

<https://www.fda.gov/drugs/developmentapprovalprocess/developmentresources/druginteractionslabeling/ucm093664.htm>

6.8.2.3 Statins

Several lipid-lowering agents (statins) are metabolized by CYP3A (simvastatin, lovastatin, atorvastatin) and/or transported by BCRP (rosuvastatin, atorvastatin) and thus may be affected by drug-drug interaction with fenebrutinib. Therefore, dose adjustments of these medications should be considered (Kellick et al. 2014) as follows:

- Simvastatin: recommended maximum dose of 10 mg/day
- Lovastatin: recommended maximum dose of 20 mg/day
- Rosuvastatin: recommended maximum dose of 10 mg/day
- Atorvastatin: recommended maximum dose of 20 mg/day

The use of statins has been associated with myopathy, which can manifest as weakness, tenderness, or muscle pain with elevations of creatine kinase $> 10 \times$ ULN. In severe cases, myopathy can cause rhabdomyolysis with or without acute kidney injury secondary to myoglobinuria, and rare fatalities due to rhabdomyolysis have occurred. The risk of myopathy is increased by elevated plasma levels of statins. Predisposing factors for myopathy include advanced age (≥ 65 years), female sex, uncontrolled hypothyroidism, renal impairment, or the use of concomitant medications that increase the plasma levels of the statin.

6.8.2.4 Herbal Therapies

For the purposes of this study, dietary supplements are defined as vitamins, minerals, purified food substances, and herbals with pharmaceutical properties.

Vitamins, minerals, and purified food substances are allowed in amounts not known to be associated with adverse effects (e.g., hypervitaminosis). Herbal therapies with pharmaceutical properties are allowed only if there is acceptable evidence of no CYP3A inhibition or induction (see Section 6.8.3 for a list of prohibited concomitant medications, including herbal products). Herbal therapies with pharmaceutical properties must not be administered during the study, unless there are sufficient data available to ascertain there are no drug interactions with fenebrutinib. Any questions can be directed to the Medical Monitor.

6.8.3 Prohibited Therapy

The results of Study GP39616 suggest that fenebrutinib can be classified as a moderately sensitive substrate of CYP3A at clinically relevant doses. There is a potential for a drug-drug interaction with any medication that strongly inhibits or induces this enzyme. Therefore, medications in the following categories should be prohibited for 7 days or 5 half-lives, whichever is longer, prior to the first dose of study drug and until the final dose of study drug.

- Strong CYP3A4 inhibitors
- Strong or moderate CYP3A inducers

The results of study (GP39616) suggest that fenebrutinib can be classified as a mild inhibitor of CYP3A at clinically relevant doses. Fenebrutinib may increase plasma concentrations of the medications in the following category. Therefore, the following medications should be prohibited during study treatment:

- CYP3A4 substrates with a narrow therapeutic window

Table 7 summarizes a list of prohibited medications for the reasons listed above. This list is not comprehensive, and the investigator should consult local prescribing information for the concomitant medication as well as the Internet reference provided below when determining whether a concomitant medication can be safely administered with study treatment. In addition, the investigator should contact the Medical Monitor if questions arise regarding medications not listed.

<https://www.fda.gov/drugs/developmentapprovalprocess/developmentresources/druginteractionslabeling/ucm093664.htm>

Table 7 List of Prohibited Medicines Due to CYP3A-Mediated Drug Interactions

Class	Examples of Drugs in this Class
Strong CYP3A4 inhibitors	Boceprevir, cobicistat, clarithromycin, danoprevir/ritonavir, elvitegravir/ritonavir, indinavir/ritonavir, itraconazole, idelalisib, ketoconazole, lopinavir/ritonavir, nefazodone, nelfinavir, posaconazole, ritonavir, saquinavir, telaprevir, telithromycin, voriconazole, and nirmatrelvir/ritonavir.
Strong CYP3A inducers	Apalutamide, carbamazepine, enzalutamide, mitotane, phenytoin, rifampin, and hyperforin (St. John's Wort)
Moderate CYP3A inducers	Bosentan, dexamethasone, efavirenz, etravirine, phenobarbital, primidone, phenobarbital, and rifabutin
CYP3A4 substrate with a narrow therapeutic window	Alfentanil, astemizole, cyclosporine, cisapride, dihydroergotamine, ergotamine, everolimus, fentanyl, pimozone, quinidine, sirolimus, terfenadine, and tacrolimus

Note: This list is not comprehensive, and the investigator should consult local prescribing information for the concomitant medication as well as the Internet reference provided below when determining whether a concomitant medication can be safely administered with study treatment. In addition, the investigator should contact the Medical Monitor if questions arise regarding medications not listed.

<https://www.fda.gov/drugs/developmentapprovalprocess/developmentresources/druginteractionslabeling/ucm093664.htm>

6.8.3.1 Other Prohibited Therapies

Use of the following concomitant therapies is prohibited as described below for participants in the DBT phase, OLE phase, and SFU phase:

- Investigational therapy (other than protocolmandated study treatment)

- Any Bcell targeted therapy (e.g., rituximab, alemtuzumab, atacicept, belimumab, ublituximab, ofatumumab, or ocrelizumab)
- BTK inhibitors (other than fenebrutinib)
- Any other DMT for MS (including, but not limited to, cladribine, mitoxantrone, interferons, glatiramer acetate, dimethyl fumarate and other fumarates, and fingolimod and other sphingosine-1-phosphate receptor modulators)

The Medical Monitor should be consulted if it is unclear if a medication is considered disease modifying.

- Systemic anticoagulation (oral or injectable) or antiplatelet agent other than nonsteroidal antiinflammatory drugs, aspirin, and other salicylates (aspirin up to 162 mg four times a day (QID) is allowed)
- Use of “as needed” doses of acid-reducing agents (e.g., PPIs, H₂RAs) at visits requiring PK sampling is prohibited (chronic dosing is acceptable) (see [Table 3](#))
- *High-dose biotin*

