Participants must not initiate PPIs or H₂RAs within 2 weeks prior to randomization.

- Treatment with IVIg or plasmapheresis within 12 weeks prior to randomization
- Sensitivity or intolerance to any ingredient (including excipients) of fenebrutinib
- Receipt of a live-attenuated vaccine within 6 weeks prior to randomization. Influenza vaccination is permitted if the inactivated vaccine formulation is administered.
- Need for systemic anticoagulation (oral or injectable) or anti-platelet agent other than nonsteroidal anti-inflammatory drugs, aspirin, and other salicylates (aspirin up to 162 mg QD is allowed)
- Previous treatment with fenebrutinib or another BTK inhibitor for any indication
- Treatment with strong CYP3A4 inhibitors, strong or moderate CYP3A4 inducers, within 7 days or 5 drug-elimination half-lives (whichever is longer) prior to randomization
- Treatment with CYP3A4 substrates with a narrow therapeutic window within 7 days or 5 drug-elimination half-lives (whichever is longer) prior to randomization
- Previous use of anti-CD20 therapies, unless the last infusion was more than 2 years prior to screening and B-cell count is normal at screening
- Previous use of fingolimod, siponimod, ozanimod, or ponesimod within 6 weeks of randomization
- Previous use of natalizumab within 6 months of randomization
- Previous treatment with azathioprine, mycophenolate mofetil, or methotrexate within 12 weeks of randomization
- Previous use of teriflunomide, unless teriflunomide plasma concentrations are <0.02 mg/L at screening
- Any previous treatment with cladribine, mitoxantrone, daclizumab, alemtuzumab, or cyclophosphamide
- Treatment with dimethyl fumarate or monomethyl fumarate within 4 weeks of randomization
- Treatment with any investigational agent within 5 half-lives of randomization
- Requirement for any prohibited concomitant medications
- Previous treatment with any other immunomodulatory or immunosuppressive medication not already listed above without appropriate washout as described in the applicable local label

If the washout requirements are not described in the applicable local label, then the wash out period must be 5 times the half-life of the medication. The PD

effects of the previous medication must also be considered when determining the required time for washout.

Note: No washout is required for interferon or glatiramer acetate.

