- An episode of torsade de pointes or a new ECG finding of clinical concern or sustained (at least two ECG measurements > 30 minutes apart) QTcF that is > 500 ms and/or > 60 ms longer than the baseline value (unless there is a clear alternative cause other than study drug) as described in [Appendix 6](#). Electrocardiogram assessment should be conducted as outlined in [Section 8.2.3](#).
- Requirement of *chronic use* of any prohibited medication as defined in [Section 6.8.3](#). *If any prohibited medication is considered to be medically necessary, the investigator should discuss with the Medical Monitor.*

The primary reason for study treatment discontinuation should be documented on the appropriate eCRF.

Refer to the schedule of activities in [Section 1.3](#) (see [Table 1](#)) for details on follow-up assessments to be performed for participants who permanently discontinue study treatment. If a participant requests to be withdrawn from treatment or follow-up assessments, this request must be documented in the source documents and signed by the investigator.

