Guidelines for management of study treatment in the event of hepatic transaminase elevations/hepatotoxicity is observed in participants are provided in [Table A6-1](#) and [Appendix 7](#), and refer to the Fenebrutinib Investigator's Brochure for further details.

A6–1.4 EFFECT ON VACCINATIONS

The effect of fenebrutinib upon the efficacy of vaccinations is unknown. It is recommended that appropriate vaccinations for per local guidelines be up to date before study participation. Refer to Section 5.2 for the exclusion criteria and Section 6.8.5 for vaccination requirements. In addition, immunization with a live or live-attenuated vaccine is prohibited for the duration of study participation, including during the safety follow-up (SFU).

A6–1.5 BLEEDING

The effect of BTK inhibition as a potential risk factor for bleeding is unknown. Bleeding was not observed in nonclinical studies with fenebrutinib. Bleeding events, including Grade ≥ 3 GI bleeding, have been reported in participants with hematological cancer treated with fenebrutinib, and Grade ≥ 2 bleeding has been reported in participants enrolled in blinded studies for autoimmune diseases.

See Section 5.1 and Section 5.2 for inclusion and exclusion criteria regarding bleeding risk. Participants should be advised to seek immediate medical attention if they develop signs and symptoms suggestive of clinically significant bleeding.

Guidelines for management of study treatment in the event that bleeding is observed in participants are provided in Table A6-1. Refer to the Fenebrutinib Investigator's Brochure for further details.

A6–1.6 CYTOPENIAS

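### The on-study aspirin cap in Protocol Section 6.8.3.1 (162 mg four times a day, 648 mg/day) is four times the entry cap in Section 5.2 (162 mg once a day), with no reason given

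*Protocol*

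**What the plan says.** Two sections of the protocol limit aspirin.

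- **Section 5.2, Exclusion Criteria (entry).** The criterion is "Need for systemic anticoagulation (oral or injectable) or anti-platelet agent other than nonsteroidal anti-inflammatory drugs, aspirin, and other salicylates", followed by the dose limit "aspirin up to 162 mg QD is allowed".
- **Section 6.8.3.1, Other Prohibited Therapies (on study).** Almost the same clause is applied to "participants in the DBT phase, OLE phase, and SFU phase", but the limit reads "aspirin up to 162 mg four times a day (QID) is allowed".

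Three other sections bear on the point.

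- **Section 7.1** requires permanent discontinuation of study treatment for chronic use "of any prohibited medication as defined in" Section 6.8.3, of which 6.8.3.1 is a part.
- **Appendix 6, A6-1.5 (Bleeding)** tells the reader: "See Section 5.1 and Section 5.2 for inclusion and exclusion criteria regarding bleeding risk". It mentions no aspirin dose of its own.
- **Section 6.8** requires the following to be recorded for each concomitant medication: "Dosage information, including dose and frequency".

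**The concern.** An aspirin cap in a trial of a BTK inhibitor exists because of what may happen when the two drugs are taken together. Here the tighter limit applies before exposure and the looser one during it. A candidate who needs 324 mg/day (2 × 162 mg) is over the entry allowance, yet a participant may start that same dose after randomization and remain within the protocol.

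Bleeding risk is at stake. A6-1.5 treats the contribution of BTK inhibition to bleeding as unknown. It reports no bleeding in nonclinical work, Grade 3 or higher GI bleeding in fenebrutinib-treated patients with hematological cancer, and Grade 2 or higher bleeding in blinded autoimmune studies (arm not stated). Table A6-1 continues dosing through Grade 1 and 2 bleeding and withholds study drug only from Grade 3. Limits on co-medication are therefore among the preventive controls that remain once dosing starts.

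The wording also has a direct operational effect. Aspirin expressly allowed by 6.8.3.1 is not prohibited medication, so chronic use within that allowance cannot trigger the Section 7.1 rule.

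**Working it through.** The plan states no daily total, so there is no figure of its own to reproduce. The check is arithmetic on the two limits, followed by a search for a reason.

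**1. Daily dose.** Daily maximum = unit dose × doses per day.

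| Section | Applies to | Limit | Daily maximum |
|---|---|---|---|
| 5.2 | Entry | 162 mg once a day | 162 × 1 = 162 mg |
| 6.8.3.1 | Double-blind, open-label extension, safety follow-up | 162 mg four times a day | 162 × 4 = 648 mg |

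Ratio: 648 / 162 = 4.0. Excess: 648 − 162 = 486 mg/day. If 6.8.3.1 were aligned to once daily, both sections would give 162 mg/day and the ratio would be 1.

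**2. Is it a reading error in the text?** Unlikely. Section 6.8.3.1 gives the frequency in words and again as an abbreviation.

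**3. Is a reason given?** None was found in the bleeding text (A6-1.5), the management guidelines (Table A6-1), the rationale for the current amendment or the amendment history (Appendix 12). The protocol marks substantive new information in italics. In 6.8.3.1 the high-dose biotin item is italic and the aspirin item is not, so nothing marks the four-times-daily limit as a deliberate change in this version.

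**4. Which limit does the safety plan rely on?** A6-1.5 sends the reader to Sections 5.1 and 5.2. The only aspirin limit there is 162 mg once a day.

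**5. How long does the looser limit apply?** Up to 12 weeks of double-blind treatment and up to 192 weeks of open-label fenebrutinib. It also covers the safety follow-up of about 4 weeks, when study drug has stopped.

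**6. How many people?** Only participants taking more than 162 mg/day on study matter, and the documents do not give that number. The rates below are assumptions chosen to show a range, applied to the planned 102 participants, 68 of them on fenebrutinib.

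| Assumed share above 162 mg/day | Of 102 participants | Of 68 on fenebrutinib |
|---|---|---|
| 0% | 0 | 0 |
| 1% | 1.0 | 0.7 |
| 5% | 5.1 | 3.4 |
| 10% | 10.2 | 6.8 |

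**The case against.** The strongest reply is that the two limits govern different periods, so a site can comply with both and there is no formal contradiction. That is correct. It does not explain why the limit should loosen when exposure begins.

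Intent is also unproven. A mis-expanded QD is an inference, and A6-1.5 refers to the Investigator's Brochure, which is not available here and might hold a rationale. This stands, and it is why the sponsor should be free to justify 648 mg/day instead of correcting it.

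The safety gain is small. NSAIDs and other salicylates are exempt without a dose cap in both sections. Other safeguards exist:

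- entry exclusions for low platelets, for hospitalization or transfusion for a GI bleed, and for known bleeding diathesis;
- stopping rules for thrombocytopenia;
- prompt reporting of bleeding by participants;
- withholding study drug for Grade 3 or higher bleeding;
- a general provision in Section 7.1 to stop treatment when safety may be jeopardized.

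Section 5.2 should also keep out people who already need more than 162 mg/day, so higher doses arise mainly when aspirin is started or increased after enrolment. Paracetamol up to 2 g/day is available as an alternative analgesic. All of this stands and limits the size of the benefit.

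Finally, tightening a limit may count as a substantial amendment needing ethics and health authority approval across about 35 sites. It would also bring chronic users under the Section 7.1 rule, and MRI data after treatment withdrawal are censored in the primary analysis. Applying the correction prospectively avoids penalizing anyone who followed the approved text, and few participants are likely to be involved.

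**Conclusion.** The concern holds and should be fixed. The on-study aspirin limit is four times the entry limit (648 against 162 mg/day), the two sit in near-identical clauses, and neither the protocol nor the SAP gives a reason. This is an operative dose limit that sets the threshold for a discontinuation rule, so it is more than a cosmetic slip.

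Confidence in the discrepancy is high. That once daily was intended is only the likeliest reading. The practical effect depends on how many participants take more than 162 mg/day on study, which is unknown and may be none. Nothing in the efficacy analysis, sample size, power or error control changes.

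**What to change.** Amend Section 6.8.3.1 so that aspirin is allowed up to 162 mg once daily (QD), matching Section 5.2. If 648 mg/day is intended on study, state this explicitly and give the safety rationale for a looser limit than at entry.

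Send sites a clarification letter, and apply the corrected limit from that date forward. Compare recorded aspirin dose and frequency with the corrected limit to find participants who need review. Earlier use within the approved text should not be treated as a deviation.

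The cost is one line of protocol text and the letter, plus whatever approval the amendment needs locally. Dose and frequency are already collected under Section 6.8, so no new data are required, and the design and SAP stay as they are.
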